1.5 MODIFICATIONS TO THE STATISTICAL SECTION OF THE PROTOCOL

The statistical section of the protocol was never changed in an amendment.

The protocol history table below gives the timing, rationale and key details of major changes to the protocol statistical section.

Amendment Number	Date Approved	Rationale	Description of statistical changes
NA	NA	Modification of basal insulin dose (U and U/kg body weight) analysis	MMRM analysis for the change from baseline to Week 12 and Week 24 of basal insulin dose will be replaced by a descriptive analysis.
NA	NA	Modification of basal insulin doses section	Basal insulin dose was included in the Section 2.4.3.1
NA	NA	Modification of analysis in 8-point SMPG profiles per time-point	MMRM analysis for the change in 8-point SMPG profiles per time-point from baseline to Week 12 and Week 24 was removed. Only a descriptive analysis will be performed.
NA	NA	Modification of analysis in 4-point SMPG profiles per time-point	MMRM analysis for the change in 4-point SMPG profiles per time-point from baseline to Week 12 and Week 24 was removed. Only a descriptive analysis will be performed.

1.6 STATISTICAL MODIFICATIONS MADE IN THE STATISTICAL ANALYSIS PLAN

There was no Statistical Analysis Plan amendment.

2 STATISTICAL AND ANALYTICAL PROCEDURES

2.1 ANALYSIS ENDPOINTS

2.1.1 Demographic and baseline characteristics

The baseline value is defined as the last available value prior to the first injection of open-label IMP.

For randomized and not treated patient, the baseline value is defined as the last available value obtained up to the date and time of randomization.

All baseline safety and efficacy parameters (apart from those listed below) are presented along with the summary statistics in the safety and efficacy sections (Section 2.4.5 and Section 2.4.4).

Demographic characteristics

- Age (years),
- Age qualitative categories: <65, ≥ 65 years
- Gender (Male, Female),
- Baseline body weight (kg),
- Baseline body weight (kg: <50, ≥ 50 and <100, ≥ 100 kg,
- Baseline Body Mass Index (kg/m²),
- Baseline body mass index (BMI) categories (kg/m^2) : $<30, \ge 30 35 <, \ge 35 kg/m^2$,
- Baseline estimated glomerular filtration rate ([GFR], using modification of diet in renal disease [MDRD] formula, mL/min/1.73m²),
- Baseline estimated glomerular filtration rate (GFR, using MDRD formula, mL/min/1.73m²) : <15 End stage, ≥15 and <30 Severe decrease, ≥30 and <60) Medium decrease, ≥60 and <90) Mild decrease, ≥ 90 Normal,
- Randomization strata of screening HbA1c categories ($< 8.0; \ge 8.0\%$),
- Randomization strata of Sulphonylurea (SU) or meglitinides use before the day of screening (Yes; No).

Medical or surgical history

Medical / surgical history includes patient's allergy history.

This information, pre-listed or not in the e-CRF, will be coded using the version of Medical Dictionary for Regulatory Activities (MedDRA) currently in effect at Sanofi at the time of database lock.

Disease characteristics at baseline

Specific disease history includes:

- Duration of diabetes (years),
- Category of duration of diabetes ($<10, \ge 10$ years),
- Age (years) at onset of diabetes,
- Previous non-insulin antihyperglycemic treatment:
 - Duration of previous non-insulin antihyperglycemic treatment (years),
 - Previous non-insulin antihyperglycemic treatment (yes /no),
 - Number of previous non-insulin antihyperglycemic agent (0, 1, 2, >2),
 - Previous non-insulin antihyperglycemic treatment (biguanides, sulfonylurea, glinides, thiazolidinediones, DDP-4 inhibitors, SGLT-2 inhibitors, GLP1-RA, alpha-glucosidase inhibitors, other),
- Diabetic microvascular complications (yes or no):
 - Diabetic retinopathy (yes/no/unknown), photocoagulation performed (yes/no/unknown) and vitrectomy performed because of diabetic retinopathy (yes/no/unknown),
 - Diabetic neuropathy (yes/no/unknown),
 - Diabetic nephropathy (yes/no/unknown) including the most recent event categories (microalbuminuria, overt proteinuria or impaired renal function).

Baseline efficacy data

The following baseline efficacy data will be provided:

- HbA1c (% and mmol/mol),
- FPG (mmol/L and mg/dL),
- Mean of SMPG (mmol/L and mg/dL) from 8-point profiles measured on a 24-hour period, and SMPG per time-point,
- Average pre-breakfast SMPG (mmol/L and mg/dL) = mean of pre-breakfast (fasting).

SMPG values in the last 7 days prior the 1st IMP (see Section 2.5.2).

Other baseline efficacy endpoints are presented along with the summary statistics.

Basal insulin at baseline

Basal insulin daily dose (U and U/kg): Is equal to the actual starting IMP dose of basal insulin as reported by the investigator into the e-CRF (first IMP intake).

Smoking/alcohol habits

- Tobacco habits (never, quit smoking, currently smokes) including the average number of cigarettes per day,
- Alcohol habits (never, at least monthly, at least weekly, at least daily) including the number of daily standard drink (1 or 2, > 2).

Any technical details related to computation, dates, and imputation for missing dates are described in Section 2.5.

Other baseline characteristics (such as quality of life/health economic endpoints) are presented along with the summary statistics.

2.1.2 **Prior or concomitant medications**

All medications taken within the past 3 months before screening and until the end of the study are to be reported in the case report form pages.

All medications will be coded using the World Health Organization-Drug Dictionary (WHO-DD) using the version currently in effect at Sanofi at the time of database lock.

- Prior medications are those the patient used within 3 months and from screening to first investigational medicinal product (IMP) intake. Prior medications can be discontinued before first administration or can be ongoing during treatment phase.
- Concomitant medications are any treatments received by the patient concomitantly to the IMP, from first injection of IMP to the last injection of IMP+7 days (0 day for antidiabetic therapy). A given medication can be classified both as a prior medication and as a concomitant medication. Concomitant medications do not include medications started during the post-treatment period (as defined in the observation period in Section 2.1.4).
- Post-treatment medications are those the patient continued or started on or after 8 days (1 day for antidiabetic therapy) after the last dose of open-label IMP.

Anti-diabetic medication will be identified by a pre-defined list of anatomic therapeutic chemical (ATC) codes (see in Appendix B).

Any technical details related to computation, dates, imputation for missing dates are described in Section 2.5.

Rescue therapy:

Routine fasting SMPG, central laboratory FPG measurements and central laboratory alerts on HbA1c are set up to ensure that glycemic parameters remain under predefined threshold values. The threshold values for rescue are defined as follows:

From visit 14 (Week 12): FPG >200 mg/dL (11 mmol/L) and / or HbA1c >8.5%.

In case of FPG or HbA1c above the thresholds, the investigator should ensure that no reasonable explanation exists for insufficient glucose control and in particular that:

- Plasma glucose was actually measured in fasting condition (ie, After at least 8 hours fasting),
- Study treatment is being properly titrated according to the protocol,
- There is no intercurrent disease which may jeopardize glycemic control (eg, infection),
- Compliance to treatment, diet and lifestyle is appropriate.

If any of the above can reasonably explains the insufficient glycemic control, the investigator should undertake appropriate action, ie,:

- Titrate basal insulin dose according to the protocol,
- Initiate an evaluation and treatment of any intercurrent disease (to be reported in AE/SAE/concomitant medication parts of the e-CRF and the medical record),
- Stress the absolute need to comply with treatment, diet and lifestyle recommendations,
- Schedule an HbA1c and/or FPG assessment at the next visit (if the next visit is a phone call, it should be replaced by an on-site visit).

If none of the above reasons can be found, and/or appropriate actions fail, it is recommended to initiate rescue therapy. The choice of the anti-diabetic treatment to be added to the basal insulin should be based on Investigator's decision and local labeling documents. Adding prandial insulin may be the preferred option. The addition of a new antidiabetic drug or increase in dose of background antidiabetic medication ("rescue") should not be decided based on a single FPG or HbA1c value but be based on a thorough evaluation of the patient's glycemic control.

Note: Short-term (up to 10 days maximum) uses of short/rapid-acting insulin therapy (eg, due to acute illness or surgery) will not be considered as rescue therapy.

All assessments for primary and secondary efficacy and safety parameters planned in final on treatment assessment visit (Visit 20) should be performed before adding the "rescue medication". Then the patient continues the IMP and stays in the study in order to collect safety information.

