#### 8.2.4 Starting dose and dose adjustments

#### Starting dose

The recommended daily starting dose of each IMP is defined per label with once daily as below followed by individual dose adjustment:

- Toujeo: 0.2 units/kg (4)
- Tresiba: 10 units (5)

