#### Dose adjustment

During the study, doses of either basal insulin, Toujeo or Tresiba will be titrated to achieve glycemic targets without hypoglycemia according to the same algorithm as below (Table 2).

- After randomization, the dose will be titrated at least weekly (but no more often than every 3 days), until the patient reaches a target fasting SMPG of 80 to 100 mg/dL (4.4 to 5.6 mmol/L) while avoiding hypoglycemia episodes.
- Thereafter, until the end of the study, the dose will be adjusted as necessary to maintain this fasting SMPG target.
- Dose adjustments are based on a median of fasting SMPG values from the last 3 measurements, which include the value measured on the day of titration, measured by the patient using glucometers and accessories supplied by the sponsor.

The best efforts should be made to reach the target glucose by 8-12 weeks after randomization.

Median a of fasting SMPG (mg/dL)from the last 3 measurements	Toujeo ® and Tresiba ® dose change b
>140 (7.8 mmol/L)	+ 6 U
>120 and ≤140 (>6.7 and ≤7.8 mmol/L)	+ 4 U
>100 and ≤120 (>5.6 and ≤6.7 mmol/L)	+ 2 U
≥80 and ≤100 (>4.4 and ≤5.6 mmol/L)	No change
<80(<4.4 mmol/L) or occurrence of 1 symptomatic confirmed hypoglycemia episode documented in the preceding week	-2U or at the discretion of the investigator

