#### COMPENSATION FOR LACK OF BLINDING

Despite the open-label administration of IMP, assessment of outcomes will be based on objectively collected data, which are assessments for the efficacy variable (HbA1c, FPG) by central laboratory blinded to study treatment groups.

As Toujeo and the control drug Tresiba are distinguishable in terms of initial dose and following doses during the first weeks of the study, a process will be applied to blind this information at the sponsor study team level.

The sponsor study team, except individuals who have access to patients' source documents (eg, local monitoring team, auditors) will remain blinded to the treatment arm of individual patients and dose of IMP throughout the study up to the database lock. All analyses and data review before database lock will be performed blindly, except for the titration review which will be performed by an independent reviewer.

Insulin titration review will be performed by reviewing the data related to fasting SMPG, hypoglycemia events and IMP dose titration by independent reviewer.

The first Statistical Analysis Plan (SAP) will be written before the first patient is randomized in the study.

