# 9.2 SECONDARY ENDPOINTS

#### 9.2.1 Secondary efficacy endpoint(s)

- Change in HbA1c from baseline to Week 12,
- Change in FPG from baseline to Week 12 and Week 24,
- Change in fasting SMPG from baseline to Week 12 and Week 24,
- Change in 4-point SMPG and 8-point SMPG profiles per time-point from baseline to Week 12 and Week 24,

Property of the Sanofi Group - strictly confidential

- Change of mean 24-hour plasma glucose based on 8-point SMPG from baseline to Week 12 and Week 24,
- Change in variability of fasting SMPG and 24-hour plasma glucose based on 8-point SMPG from baseline to Week 12 and Week 24,
- Percentage (%) of patients reaching target HbA1c <7% and ≤6.5% at Week 12 and Week 24,
- Percentage (%) of patients reaching target HbA1c <7% and ≤6.5% at Week 12 and Week 24 without severe and/or confirmed hypoglycemia (70 mg/dL and 54 mg/dL as cut off point) during the 12 weeks and 24 weeks treatment period,
- Percentage (%) of patients with SU or meglitinide dose reduction/discontinuation due to hypoglycemia over 24 weeks of treatment,
- Percentage of patients requiring rescue therapy during 24 weeks treatment period,
- Basal insulin dose (U and U/kg body weight): change from baseline to Week 12 and Week 24.

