2.4.3.1 Basal insulin dose

Descriptive statistics of basal insulin dose (U and U/kg) will be presented including change from baseline, relative, change from baseline and change from previous visit.

For change in daily basal insulin at each visit and at endpoint (Week 12 and Week 24), a determination of the average daily insulin doses is made by using daily doses computed on a weekly basis. At each post-baseline visit, the mean daily basal insulin doses will be calculated as the mean of daily insulin doses collected over the last 7 days before the visit. No minimum number of available doses will be required.

In case of any missed doses, corresponding days should not be taken into account in the determination of the average daily insulin doses. In case of premature discontinuation or use of rescue medication, the average daily dose taken into consideration for a patient is the one measured the week before such event.

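### Basal insulin dose: the baseline is the first trial dose, whose recommended value differs by arm, so change from baseline cannot be compared between arms

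*SAP*

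**What the plan says.** **Endpoint.** Protocol 9.2.1 lists among the secondary efficacy endpoints: "Basal insulin dose (U and U/kg body weight): change from baseline to Week 12 and Week 24". SAP 2.4.4.2.1 still names it with the secondary efficacy analyses and refers to SAP 2.4.3.1. The endpoint list in SAP 2.1.3.2 omits it.

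**Baseline.** SAP 2.1.1 says that the baseline daily dose, in U and U/kg, "Is equal to the actual starting IMP dose of basal insulin as reported by the investigator into the e-CRF (first IMP intake"). The general rule in Protocol 9.2.1, at the start of SAP 2.1.1 and in SAP 2.1.3 is different: baseline is the latest value before the first injection of trial drug.

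**Starting dose.** Protocol 8.2.4 states: "The recommended daily starting dose of each IMP is defined per label with once daily as below followed by individual dose adjustment". It then gives 0.2 units/kg for Toujeo and 10 units for Tresiba. From there both arms follow one titration algorithm and one fasting glucose target. Protocol 8.4, on compensating for the lack of blinding, acknowledges the contrast: "As Toujeo and the control drug Tresiba are distinguishable in terms of initial dose and following doses during the first weeks of the study".

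**Analysis.** SAP 1.5 replaces the planned MMRM on dose change with a descriptive analysis. Under SAP 2.4.3.1, descriptive statistics of the dose "will be presented including change from baseline, relative, change from baseline and change from previous visit". The section also defines the mean daily dose at each post-baseline visit from the preceding 7 days.

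**The concern.** A baseline is normally fixed before treatment, so that randomization balances it and change from it can be compared between arms. Here the baseline is itself the first dose of randomized treatment, and its recommended value depends on the arm. Subtracting it, or dividing by it, carries the difference in starting rules into the between-arm contrast.

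A table of change by arm could then suggest that Tresiba needed more insulin when both arms finish on the same dose. It could also hide or reverse a real difference in final dose. Relative change is more exposed, because the arm-dependent quantity is the denominator. Dropping the MMRM removes the test but leaves the offset.

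**Working it through.** **The plan's own figure.** The documents derive no number for insulin dose. The one derived figure is the HbA1c sample size (SD 1.4%, margin 0.3%, true difference 0, one-sided 2.5%, 90% power). It reproduces at 458 per arm against the stated 460. Nothing below depends on it.

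**Inputs**
- Starting doses: 0.2W units (Toujeo) and 10 units (Tresiba), with W in kg (Protocol 8.2.4). Assumed to be followed as recommended.
- Baseline: the first dose taken (SAP 2.1.1).
- Weight: the documents give no mean, so 60 to 130 kg is assumed.
- Final dose F: assumed equal in the two arms, to isolate the effect of the baseline.

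**Change in units**

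Toujeo minus Tresiba = (F - 0.2W) - (F - 10) = 10 - 0.2W.

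F cancels, so the result does not depend on the assumed final dose. Because the expression is linear in W, the offset in arm means is 10 - 0.2 × mean weight if mean weights are balanced.

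**Change in U/kg** (weight held constant)

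Toujeo minus Tresiba = 10/W - 0.2.

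**Relative change**

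Toujeo: F/(0.2W) - 1. Tresiba: F/10 - 1. The ratio of the two fold-increases is 10/(0.2W) = 50/W, again whatever F is.

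| Assumed weight (kg) | Toujeo start (U) | Tresiba start (U) | Difference in change (U) | Difference in change (U/kg) | Relative change, Toujeo vs Tresiba, if both end at 40 U (assumed) |
|---|---|---|---|---|---|
| 60 | 12 | 10 | -2 | -0.033 | +233% vs +300% |
| 70 | 14 | 10 | -4 | -0.057 | +186% vs +300% |
| 90 | 18 | 10 | -8 | -0.089 | +122% vs +300% |
| 110 | 22 | 10 | -12 | -0.109 | +82% vs +300% |
| 130 | 26 | 10 | -16 | -0.123 | +54% vs +300% |

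**Does it average out?** The offset is zero only where 0.2W = 10, that is at 50 kg. Exclusion E 08 removes patients with BMI below 25 kg/m². At BMI 25, 50 kg corresponds to a height of √(50/25) = 1.41 m, so any eligible patient taller than that weighs more than 50 kg. Nearly every patient shifts the contrast the same way, towards a smaller apparent increase with Toujeo.

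**Can the sign reverse?** Yes, whenever the final Toujeo dose is higher by less than 0.2W - 10 units. At 90 kg, suppose Toujeo ends at 45 U and Tresiba at 40 U (assumed). Change is 45 - 18 = +27 U against 40 - 10 = +30 U, so the arm on the higher final dose shows the smaller increase. To match a Tresiba relative change of +300%, Toujeo would have to reach 4 × 18 = 72 U.

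**After the fix.** Compared on dose itself, equal final doses give F - F = 0 in U and in U/kg at every weight. In insulin-naive patients the general baseline rule gives essentially the same answer, because the dose before the first injection is about 0 U in both arms.

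**The case against.** The case for leaving the plan alone has four parts.

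- **No formal comparison is biased.** SAP 1.5 and 2.4.3.1 make this a descriptive summary within the exposure section. No between-arm estimate, confidence interval or p-value is planned for it, and SAP 2.1.3.2 no longer lists it. This stands and limits the weight of the point. A reader might infer that the non-inferiority conclusion or a tested secondary result is affected; the documents do not support that.
- **Final doses are visible.** SAP 2.4.3.1 presents the dose itself in U and U/kg, and the starting dose is among the baseline parameters. This also stands. It makes the fix cheap, but it does not settle which measure should be used to compare the arms.
- **Change from first dose is true.** An arm that goes from 10 to 40 U really was raised by 30 U. A reader might infer that the change columns are an artefact or an error; they are not. They describe titration correctly within each arm, and mislead only when the arm contrast is read as a difference in insulin requirement.
- **The starting doses are recommendations.** SAP 2.1.1 uses the dose actually taken. A reader might treat the offset as fixed by randomization at exactly 10 - 0.2W; the documents support it only as an approximation.

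What the objection does not remove is that Protocol 9.2.1 and SAP 2.4.4.2.1 keep change from baseline as a secondary efficacy endpoint, and the SAP tabulates it by arm with no caution. Nor does the SAP explain why the dose baseline departs from its general rule.

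**Conclusion.** The point holds within narrow limits. Change and relative change in basal insulin dose, as defined, contain a between-arm difference of about 10 - 0.2W units when final doses are equal: about -4, -8 and -12 U (Toujeo minus Tresiba) at 70, 90 and 110 kg. This rests on assumed weights and on patients starting at the recommended doses; the actual gap will follow the doses actually started.

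The consequence is confined to the change columns of an untested descriptive summary. The HbA1c analysis is unaffected. A reader might also infer that the different starting doses are a fault, or that the baseline was chosen to favour one product. The documents support neither: the protocol says that the starting doses follow each label, and no motive for the baseline definition is given. The point concerns only which quantity is used to compare the arms.

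**What to change.** 1. In SAP 2.4.3.1, and where SAP 2.4.4.2.1 refers to it, make mean daily basal dose (U and U/kg) at Weeks 12 and 24 the measure for comparing arms.
2. Keep change and relative change from first dose as within-arm summaries of titration. Footnote the tables to say that these columns are not comparable between arms because the recommended starting doses differ.
3. Reconcile the dose baseline in SAP 2.1.1 with the general rule in Protocol 9.2.1, SAP 2.1.1 and SAP 2.1.3, for example by declaring it an exception used only to describe titration. Record the change in SAP 1.5, since the protocol endpoint is worded as change from baseline.

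The cost is SAP wording and a table footnote. The visit doses are already derived under SAP 2.4.3.1, so no new data or model is needed, and dosing and titration are untouched.

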2.1.3 Efficacy endpoints

The baseline value for efficacy endpoints is the last available value prior to the first injection of open-label IMP.

HbA1c and FPG are measured at a central laboratory, for scheduled (see study flowchart in Table 1) and unscheduled time points.

Patients measure their SMPG using the blood glucometer and document them into the diary. The following SMPG values are copied in the eCRF (see study flowchart in Table 1).

In case of premature and permanent IMP discontinuation, patients should have a visit as soon as possible with the assessments normally planned in Visit 20 (Week 24). Afterward, the patients should continue in the study up to the scheduled date of study completion. They should be followed up according to the study procedures as specified in the protocol (except for the 7-day safety post-treatment follow-up).

In case of premature permanent IMP discontinuation or rescue therapy intake, the process described in Section 2.5.4 will be applied to retrieve efficacy assessments performed at the end of treatment visit or at pre-rescue visit.

Observation period of efficacy endpoints

- The 24-week on-treatment period (used to assess the on-treatment estimand) for efficacy endpoints (primary and secondary efficacy endpoints) is defined as the time from the first injection dose of open-label IMP up to:
 - 7 days after date of last IMP administration for HbA1c, or up to the introduction of the rescue therapy, whichever is earlier for the patient,
 - 0 day after date of last IMP administration for 4-point and 8-point SMPG and insulin dose, or up to the introduction of the rescue therapy, whichever is earlier for the patient,
 - 1 day after date of last IMP administration for FPG and fasting SMPG, or up to the introduction of the rescue therapy, whichever is earlier for the patient,
 - 2 days after date of last IMP administration for hypoglycemia or up to the introduction of rescue therapy, whichever is earlier for the patient,
- **The randomized 24–week period** (used to assess the intent-to-treat [ITT] estimand) for efficacy variables is defined from first dose of IMP up to Week 24, (visit 20), regardless of study treatment discontinuation and intake of rescue therapy.

